A combined total of 642 NPS applications have been delivered to 71 adult Subjects. Anatomic locations included abdomens, backs, arms, legs and faces. Discomfort was managed with localized Lidocaine. For 58 of the Subjects a favorable therapeutic outcome was established in a significant majority. Side effects consisted of relatively

minor reactions consistent with routine wound healing. No complications or adverse events were reported.

PROPOSED SEBACEOUS HYPERPLASIA STUDY

Study Design

Sebaceous Hyperplasia (SH) is a common condition that appears as white or lightly pigmented bumps or bulges on the skin that occur when hyperactive sebaceous glands produce excess oil (sebum) that pushes up on the skin surface. These benign SH lesions are more likely to occur in middle-aged and older people, but they can show up at any age. There is currently no permanent cure for sebaceous hyperplasia.

A sebaceous hyperplasia lesion is benign and painless, and does not usually require medical treatment. However, many patients choose to have them removed by physicians for cosmetic reasons, especially if the bumps are viewed as unsightly or embarrassing. . Various modalities are available to improve the appearance of SH lesions, but a few sessions or multiple applications are often required for full removal and prevention of rapid recurrence. Remedies include topical Retinol, facial peels, laser therapy, cryotherapy, electrotherapy, photodynamic therapy, excisional surgery, antiandrogen medications, and a variety of home/over-the-counter remedies.

The proposed SH Study using NPS treatment of individual lesions is a prospective, open label, multi-center non-significant risk study design where each Subject serves as his or her own control. A Principle Investigator (PI) will be identified at up to 4 participating study centers. A total of up to 75 Subjects will be consented and enrolled with an anticipated enrollment expected to be uniformly distributed across sites. The PI will consider the study inclusion and exclusion criteria and invite appropriate patients to participate in the study.

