The intended treatment device is described as the Nano-Pulse Stimulation (NPS) device and has been used in a similar manner in prior studies of skin lesion clearance. For the proposed SH lesion study, the skin contacting device component referred to as the “tip” will be generally be 1.5mm x1.5mm or 2.5 mm x 2.5mm in size with energy settings in the mid-range of previously tested energy levels. Local anesthetic in the treatment area will be used as needed to manage potential treatment discomfort.

Each Subject may present with a minimum of 2 and up to 4 designated SH lesions, with one lesion designated as an untreated control by a randomized method. All treated lesions will receive at least one NPS treatment. At 30 days post-treatment, if any treated lesion that is rated by the investigator as *Not Clear* or *Partially Clear* on a study standardized scale will be eligible for a second treatment to enhance lesion clearing. If a second treatment is indicated for some or all of the lesions the second treatment will occur at 30 days after the initial treatment. Total study time for these Subjects with any lesion requiring two treatments will be 90 days. Subjects with all treated lesions requiring only one treatment will complete the study in 60 days.

No significant risk is posed by either the use of the NPS or the study process. While safety can never be taken lightly, this study is not meant to measure monitor or analyze any significant disease or disorder for which medical treatment is mandatory.

See additional information regarding Non-Significant Risk statement below.

Non-Significant Risk Statement

The proposed study fits the criteria for a non-significant designation for the following reasons:

- Subjects will be recruited to participate in the study on a voluntary basis. Potential participants will be recruited directly from the Investigator's population of patients who are candidates for removal of their SH lesions.
- Participation in the study takes no more than approximately 1 hour for each of the maximum of 5 study visits.
- Localized anesthesia will be used to control discomfort at the time of any NPS device applications.
- After the NPS device is deployed and the anesthesia is dissipated, there may be mild, localized discomfort at the site of the treatment. A small scab or crust may develop. This occurrence is transient and should resolve without intervention.
- Prior studies support the proposal that the NPS use represents minimal risk.

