- There is no loss of privacy as no study records will be viewed or retrieved by anyone other than the study team members.
- Protected information will not be captured.
- Subject identity is protected by a coding system to de-identify them.

Study Objectives

- Per SH Lesion: NPS treated lesions will be rated via a previously used scale for similar NPS studies. At the Final Study Visit, the PI will rate each lesion in comparison to an image of that same, pre-treated lesion. At least 50% of the NPS treated lesions will be rated as "CLEAR" or "MOSTLY CLEAR".
- Per Subject: At the Final Study Visit at least 50% of the Subjects will present with 50% of their lesions rated as "CLEAR" or "MOSTLY CLEAR".
- No AE's or complications will be reported specific to the NPS device or the study process.

Success/Failure Criteria

Study outcome measures will be applied at every study visit and success/failure criteria will be applied at 60 days after the first NPS treatment for lesions treated one time or 90 days after the first NPS treatment for those lesions treated twice. Success will be determined as described in the preceding paragraph regarding Study Objectives. In patients with both single treatment lesions and multiple treatment lesions, all treated lesions will be evaluated and images captured at all visits, regardless of number of treatments

Investigator/Site Selection

Investigators/Site selection and qualification will be initiated upon IRB approval of the protocol and consent provided in this submission. Several of the potential PIs have participated in prior studies using the NPS device.

Subject Selection

Up to 75 Subjects with 2-5 qualifying SH lesions who are interested in removal of those SH lesions and meet the full study criteria will be consented to participate in a study to evaluate the outcome using the NPS device. The specific study Inclusion and Exclusion criteria are outlined in the following paragraphs.

Inclusion Criteria: (Must be a “YES” Response)

- Willing to sign the Informed Study Consent
- English speaking/reading and/or translation is available for all visits
- Males or females
- At least 18 years of age but less than 71 years of age
- Presents with at least 2 and up to 5 clinically visible SH lesions
- Understands that 1 lesion will remain untreated to act as a reference
- Lesions must measure no greater than 2.5 x 2.5 at the outside margin
- Wishes to have at least 1 and perhaps 2 NPS treatments to each study lesion

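### Success is decided by fixed 50% bars alone, with no comparison against the randomised untreated lesion; the per-Subject bar also leaves open whether that lesion is counted

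*Protocol*

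**What the plan says.** The Study Design section describes a design "where each Subject serves as his or her own control", with 2 to 4 lesions per Subject, "with one lesion designated as an untreated control by a randomized method". The inclusion criteria and the Study Process repeat the random choice, but allow up to 5 lesions and call the untreated one a reference. At each follow-up visit the untreated lesion is imaged, and every lesion is to be assessed and rated.

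Study Objectives then gives two efficacy criteria:

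- Per lesion: "At least 50% of the NPS treated lesions will be rated as" Clear or Mostly Clear.
- Per Subject: "at least 50% of the Subjects will present with 50% of their lesions rated as" Clear or Mostly Clear.

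The yardstick is each lesion's own baseline: "the PI will rate each lesion in comparison to an image of that same, pre-treated lesion". Success/Failure Criteria applies the rule at "60 days after the first NPS treatment for lesions treated one time or 90 days after the first NPS treatment" for lesions treated twice, and adds: "Success will be determined as described in the preceding paragraph regarding Study Objectives". Neither section contrasts treated with untreated lesions.

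**The concern.** A self-controlled, randomised design exists to separate the effect of treatment from change over time and from general rater optimism. Here the control is chosen at random and followed, but has no part in the decision as a comparator. The per-lesion bar is met or missed whatever happens to the untreated lesion. Rating is open label and made against a baseline photograph, so the share of untreated lesions that would be rated Clear or Mostly Clear cannot be assumed to be nil. A met bar could be reported as evidence of efficacy when it is only evidence about the treated lesions on their own.

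The second issue is the denominator of the per-Subject bar. The per-lesion bullet is limited to NPS treated lesions; the per-Subject bullet is not. Read literally, the untreated lesion counts, and it will usually count as a failure.

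**Working it through.** **Inputs.** From the protocol: up to 75 Subjects; 1 to 4 treated lesions and 1 untreated lesion each (Study Process); bars of 50%. The protocol states no expected rate, control rate, alpha or power, so there is no figure to reproduce. The prior keratosis study had 58 control lesions, but its summary reports clearance for treated lesions only. Assumed: 1-4 treated lesions equally likely (mean 2.5, so 75 × 2.5 = 187.5 treated lesions), and a within-Subject correlation of 0 to 0.33 on the clear/not-clear scale.

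**1. Per-lesion bar with no device effect (common rate p).** Approximate pass probability = P(Z > (0.50 − p)/SE), where SE = √[p(1−p)/187.5 × D] and D = 1 + (Σk²/Σk − 1) × correlation. Σk²/Σk = (1+4+9+16)/(1+2+3+4) = 3, so D runs from 1 to 1 + 2 × 0.33 = 1.66.

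- p = 0.40: SE 0.0358 to 0.0461; z = 2.80 to 2.17; pass 0.3% to 1.5%.
- p = 0.45: SE 0.0363 to 0.0468; z = 1.38 to 1.07; pass 8% to 14%.
- p = 0.50: about 50%.
- p = 0.55: by symmetry with 0.45, 86% to 92%.

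Simulation of the same model gives 0.2-1.7%, 9-15%, about 51% and 86-93%. With at most 3 treated lesions (the 4-lesion limit in Study Design), the figure at 55% is 86-90%.

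**2. Bar plus within-Subject comparison.** For each Subject, d = (treated lesions clear ÷ treated lesions) − control result (0 or 1). The test requires the lower 95% limit of mean d to exceed 0. Simulated with a true treated rate of 55%:

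| Control rate | Bar alone | Bar plus comparison |
|---|---|---|
| 10-20% | 86-93% | 86-92% |
| 30% | 86-93% | 86-90% |
| 35% | 86-93% | 77-82% |
| 40% | 86-93% | 54-69% |
| 45% | 86-93% | 29-39% |
| 50% | 86-93% | 10-14% |
| 55% (no effect) | 86-93% | 2.2-2.6% |

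These were run with each treated lesion paired to the control at that lesion's judging visit. A simpler run with one control rating per Subject, which is the form of a day-60 comparison, reproduces the main figures.

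**3. Which visit to compare at.** Whether a lesion is judged at day 60 or day 90 depends on its own day-30 rating. With no effect, rates of 55% and ratings that fluctuate between visits, bar plus same-visit comparison passes 4.4-8.7% of trials. With all lesions taken at day 60 it passes 2.3-2.6%.

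**4. Per-Subject bar, two readings** (50% read as at least 50%; control not clear).

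| Qualifying lesions | Treated | Clear needed, treated only | Clear needed, control counted |
|---|---|---|---|
| 2 | 1 | 1 | 1 |
| 3 | 2 | 1 | 2 |
| 4 | 3 | 2 | 2 |
| 5 | 4 | 2 | 3 |

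At a treated rate of 55% with independent lesions:

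- Treated only: mean chance that a Subject qualifies = (0.550 + 0.798 + 0.575 + 0.759)/4 = 0.670.
- Control counted and not clear: (0.550 + 0.303 + 0.575 + 0.391)/4 = 0.455.
- Control counted and clear: (1 + 0.798 + 0.909 + 0.759)/4 = 0.866.
- With 10% of controls clear: 0.9 × 0.455 + 0.1 × 0.866 = 0.496.

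The bar needs 38 of 75 Subjects. Treated only: z = (37.5 − 50.3)/4.07 = −3.1, pass about 99.9%. Control counted: z = (37.5 − 37.2)/4.33 = 0.07, pass about 47%. Over the correlation range, simulation gives 98-99.9% against about 47-50%.

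**The case against.** Fixed performance bars against each lesion's own baseline are a coherent choice, and several sections call the untreated lesion a reference. The background says that "a few sessions or multiple applications are often required for full removal", which makes frequent clearing without treatment unlikely; with few controls rated clear, the comparison changes nothing. This stands, and it limits the size of the point.

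A reader might infer that the bar passes an ineffective device once about 40% of untreated lesions are rated clear. It does not: with both rates at 40% the per-lesion bar passes about 1% of trials. The drop at a 40% control rate in the table is lost power against a true 15-point effect, not false success prevented. The per-Subject bar on treated lesions only is easier to pass, so this threshold belongs to the per-lesion bar.

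A reader might also infer that the control is never used or that no comparison is planned anywhere. The control is imaged, appears to be rated, and may literally enter the per-Subject denominator; an unseen SAP may add a comparison. Neither changes the success rule, which the protocol fixes without a contrast.

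That the control receives a Clear or Mostly Clear rating is inferred from the instruction to rate each lesion. The protocol does not say so expressly.

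**Conclusion.** The point holds in a conditional form. The stated success rule cannot show that treated lesions did better than the randomised untreated lesion. For the per-lesion bar, the risk of declaring success with no device effect is about 1% at a common rate of 40%, 9-15% at 45%, about 50% at 50% and 86-93% at 55%; it becomes serious from about 45-50%. The documents give no control rate and do not support a claim that it will be that high. If it is about 30% or less, the added comparison costs almost nothing. The figures assume 75 Subjects, 1-4 treated lesions equally likely and correlation up to 0.33.

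The per-Subject wording is an ambiguity rather than a proven error. Treated-only is the likelier intent, because success time points are given only for lesions treated once or twice. The literal reading would halve the pass probability in the example above. No stated number is wrong. This should be fixed.

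**What to change.** In Study Objectives and Success/Failure Criteria:

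1. Keep the 50% bars and their 60/90-day time points. Add a within-Subject comparison with the Subject as the unit: proportion of treated lesions rated Clear or Mostly Clear minus the control's 0/1 result, mean difference with 95% CI, lower limit above 0. Take all lesions at day 60, a visit every Subject attends, as the main comparison. Report same-visit pairing at day 60 or 90 as supportive only, because the visit depends on the treated lesion's own day-30 rating.
2. State that the untreated lesion is rated on the same Clear/Mostly Clear scale at each visit.
3. Limit the per-Subject bar explicitly to NPS treated lesions.

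If the untreated lesion is meant only as a visual reference, say so, and state that meeting the bars is not evidence against an untreated control.

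**Cost.** Wording and two simple analyses; no added visits or Subjects, and no added data if the control is already rated as the Study Process implies. Success becomes harder to claim if controls are often rated clear, even when the device has a true but modest effect: at 55% against 40%, about 54-69% instead of 86-93%. Day 60 falls only 30 days after a second treatment and may understate the effect in twice-treated lesions. Open-label rating can still favour treated lesions, which this comparison does not cure.

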- if 4 SH lesions are qualified, 3 will be treated and 1 will be reference
- if 5 SH lesions are qualified, 4 will be treated and 1 will be reference
- Using a randomization method the selected SH lesions will be designated to be treated and one will be designated as an untreated control
- Images of each of the selected lesions will be taken prior to anesthesia or treatment
- Local anesthesia will be applied to all study selected SH lesions
- The lesions to be entered into the study will be numerically labeled. Those lesions to be treated vs the reference lesion (non-treated) will be randomly selected.
- A light bandage and any PI recommended dressing will be applied
- Subject will be discharged

Activities on 2nd Study Visit Day – 5 Days post NPS treatment

- Images of each of the treated lesions and one non-treated lesion will be taken
- Each lesion will be clinically assessed and the appearance will be rated according to specified criteria.
- Any adverse events will be identified and documented.

Activities on 3rd Study Visit Day – 30 Days post NPS treatment

- Images of each of the treated lesions and one non-treated lesion will be taken
- Each lesion will be clinically assessed and the appearance will be rated according to specified criteria
- If any lesions are rated other than *Clear* or *Mostly Clear*, a 2nd NPS treatment may be delivered to that previously treated lesion
- Any adverse events will be identified and documented

Activities on 4th Study Visit Day – 60 Days post NPS treatment #1

- Images of each of the treated lesions and one non-treated lesion will be taken
- This is Final Study visit for any patient for whom all lesions were treated one time
- Each lesion will be clinically assessed and the appearance will be rated according to specified criteria
- Any adverse events will be identified and documented

Activities on 5th Study Visit Day – 90 Days post NPS treatment #1

- Images of each of the treated SH lesions and one non-treated SH lesion will be taken
- This is Final Study visit for any treated lesion
- Each lesion will be clinically assessed and the appearance will be rated according to specified criteria
- Any adverse events will be identified and documented

SH Study Follow-up Visit Schedule

Study Visit Interval	#1 NPS TX*	#2 5 days post NPS TX	#3 30 days post NPS TX	#4 60 days post NPS TX #1	#5 90 days post NPS TX

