Study Visit Description	TX #1	Wound Check	Wound Check TX #2 (if applicable)	Wound Check Final visit for all lesions treated only one time	Wound Check Final visit for all lesions treated more than one time
Visit Range (# of Days Post First NPS TX)		4-8 days	28-35 days	57-67 days	87-97 days

*TX = Treatment

SUBJECT COMPENSATION

Each Subject will be compensated for any inconvenience that study participation may represent. Specifically, each Subject will make 4-5 total visits to the PI's office (approximately 4-5 hrs. total time). In return for this time commitment, the Subject will receive \$200 per treatment visit, \$100 per check-up visit and \$200 for the Final Visit. An additional \$400 bonus will be paid for completing all of the scheduled visits. The total amount of compensation will be up to \$1000 to those Subjects who receive one NPS treatment and \$1200 to those Subjects who receive more than one NPS treatment.

STUDY BENEFITS

A volunteer for the proposed study is someone who has elected removal of SH lesions. Such scars are typically removed via surgical excision, intra-scar steroid injections or systemic steroids. Participation in the study offers another technique to accomplish the same thing as the typical tools. Experience with the NPS to date offers some confidence that the scars may be lessened although no assurances will be offered. The information learned may contribute to the ultimate use of a more safe and effective device available to treat benign and non-benign lesions in future patients.

STUDY/NPS DEVICE RISKS

The Investigators for the study are experienced physicians. Use of the NPS poses very minimal risk, including scabbing, minor skin pigment changes or scarring and minor discomfort which can be further minimized by covering the spot with a small bandage.

Typical wound complications such as infection, bleeding and discomfort which requires prescription medication for relief are not anticipated. If they should occur they would be considered an unanticipated adverse event and managed as such. If the Subject has any questions or concerns about their medical condition or if an unforeseen event should occur the Subject will be advised to contact the PIs or their designate.

SITE TRAINING PLANS

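### All visit windows run from the first treatment, so a lesion re-treated at visit 3 has no scheduled check for 22 to 39 days, against 4 to 8 days after treatment 1

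*Protocol*

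**What the plan says.** The table under SH Study Follow-up Visit Schedule has one row of windows, labelled "Visit Range (# of Days Post First NPS TX", with these values:

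| Visit | Purpose | Days after treatment 1 |
|---|---|---|
| 2 | Wound check | 4-8 |
| 3 | Wound check; treatment 2 if applicable | 28-35 |
| 4 | Wound check; final visit for lesions treated once | 57-67 |
| 5 | Wound check; final visit for lesions treated more than once | 87-97 |

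Study Design says that, where re-treatment is indicated, "the second treatment will occur at 30 days after the initial treatment". The activity list for visit 3 agrees: for a lesion not rated Clear or Mostly Clear, "a 2nd NPS treatment may be delivered to that previously treated lesion". The Non-Significant Risk Statement limits the time needed "for each of the maximum of 5 study visits".

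On wound events, STUDY/NPS DEVICE RISKS says: "Typical wound complications such as infection, bleeding and discomfort which requires prescription medication for relief are not anticipated". If they do occur, "they would be considered an unanticipated adverse event and managed as such". For questions or unforeseen events, "the Subject will be advised to contact the PIs or their designate". The third item under Study Objectives reads: "No AE's or complications will be reported specific to the NPS device or the study process".

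**The concern.** The sponsor scheduled a wound check with AE recording about five days after treatment 1. The same device may then be applied to the same lesion again, but the schedule does not restart and the early check is not repeated.

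The events the Protocol would treat as unanticipated AEs (infection, bleeding, pain that needs a prescription) belong largely to the first days after treatment. Attachment A cites earlier histology of treated tissue with partial healing at 5 days and full recovery by 15. A first look at 22 days or later therefore comes after that acute phase.

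Two things are at stake:

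- **Patient safety.** An infection or bleed after re-treatment meets no planned check while it is active.
- **The AE objective.** It is a single study-wide target of no reported events, covering both treatments. Weaker ascertainment after the second treatment can only move it towards being met.

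Lasting effects such as scarring or pigment change are not in question, because visits 4 and 5 can still show them.

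**Working it through.** **1. Time from treatment to the first scheduled look**

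The inputs are the schedule table's windows and the nominal days 30 and 60. Visit 4 is the right comparator for a re-treated lesion, because Success/Failure Criteria has all treated lesions evaluated and imaged at every visit.

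| | Shortest | Nominal | Longest |
|---|---|---|---|
| After treatment 1 (visit 2) | 4 | 5 | 8 |
| After treatment 2 (visit 3 to visit 4) | 57 − 35 = 22 | 60 − 30 = 30 | 67 − 28 = 39 |

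**2. Whether another visit fills the gap**

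The five-visit maximum leaves no room for one. SUBJECT COMPENSATION gives an independent check, with $200 per treatment visit, $100 per check-up, $200 for the final visit and a $400 completion bonus:

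- One treatment, four visits: 200 + 100 + 100 + 200 + 400 = $1000, the stated total.
- Two treatments, five visits: 200 + 100 + 200 + 100 + 200 + 400 = $1200, the stated total.
- One more paid check-up would make $1300, which the Protocol does not offer.

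The payments thus account for exactly five visits. No telephone contact appears in the activity lists or the table.

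**3. Possible effect on the AE objective (illustration; all inputs except the 75 Subjects are assumed)**

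Let *m* be the number of re-treated Subjects, *p* the acute AE risk per Subject per treatment session, and *d* the probability that an acute AE after treatment 2 is detected. Detection after treatment 1 is set at 100%, and sessions are taken as independent.

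- P(no AE reported), schedule as written: (1 − p)^75 × (1 − p·d)^m
- P(no AE reported), full detection after both treatments: (1 − p)^(75 + m)

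The assumed ranges are 10-50% of 75 Subjects re-treated (m = 8 to 38), p = 0.005, 0.01 or 0.02, and d = 0.5 or 0.75.

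| m | p | d | As written | Full detection | Difference |
|---|---|---|---|---|---|
| 8 | 0.005 | 0.75 | 0.666 | 0.660 | +0.007 (smallest in the grid) |
| 22 | 0.01 | 0.5 | 0.421 | 0.377 | +0.044 |
| 38 | 0.01 | 0.5 | 0.389 | 0.321 | +0.068 (largest in the grid) |

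Differences are taken before rounding.

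**4. Where an early contact would fall**

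Four to eight days after treatment 2 is day 28 + 4 = 32 to day 35 + 8 = 43 after treatment 1.

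**The case against.** The case on the other side accepts the arithmetic and disputes how much follows from it.

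- **AE capture after treatment 2 is not absent.** Visits 4 and 5 both require AEs to be documented, and Subjects are told to make contact if something goes wrong. Pain that needs a prescription involves a prescriber by definition, and a clinical infection would probably be reported or remembered a month later. This stands, and it is a reason to expect a small effect. But the same route to the investigator exists after treatment 1, where the sponsor still planned an early look.
- **Detection after treatment 1 is not complete either.** Between visits 2 and 3 there is a further gap of 28 − 8 = 20 to 35 − 4 = 31 days, and events before day 4 also depend on self-report. This stands. The real difference is one early look, so the 100% assumption makes the illustration err on the large side.
- **The anchor is not the whole cause.** Moving visits 4 and 5 to 30 and 60 days after treatment 2 would leave the gap in place. That is correct for re-anchoring those two visits alone. Restarting the full schedule at treatment 2 would have brought the early check with it.
- **The visit cap and payments count office visits, not calls.** True, and the consent pages, where aftercare instructions might sit, are not available. STUDY PROCESS also describes its activities as an example whose order may vary. None of this puts a contact into the schedule.
- **Risk is low and little turns on the objective.** The prior-study summary reports no AEs in 71 Subjects and 642 applications, lesions are small, and several higher-risk groups are excluded. The AE objective has no formal test attached. This supports a low severity and a light remedy, but it does not close the gap.

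**Conclusion.** The point holds, as a minor one. The schedule as written leaves 22 to 39 days (nominally 30) before the first planned look after treatment 2, against 4 to 8 days after treatment 1, and no listed visit or call falls between. That part is certain and needs no assumption.

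The consequence for the reported AE count is uncertain and probably modest. The range of 0.7 to 6.8 percentage points rests on assumed re-treatment shares, event risks and detection rates, none of which the Protocol supplies, and on full detection after treatment 1, which overstates the contrast. The direction is clear: any missed event favours the no-AE objective. The final-visit clearance ratings are unaffected.

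**What to change.** Add one structured telephone or photo contact by the existing site team 4 to 8 days after treatment 2 (days 32-43 after treatment 1), for re-treated Subjects only. It should ask about infection, bleeding and pain needing prescription medication, with a site visit only if a problem is reported. The five-visit schedule and the payment totals can otherwise stay as they are.

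If no contact is added, the report should limit its acute-phase safety conclusion to the first treatment.

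The cost is one short contact per re-treated Subject, plus an edit to the schedule table and the consent form. No new staff or procedure is needed. The downside is that more AEs may be recorded, so the no-AE objective may be harder to meet.
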